4.4.3 Exploratory Analyses

The following efficacy endpoints will be evaluated in the randomized patients without detectable *PIK3CA*-mutant tumors: investigator-assessed PFS, ORR, OS, CBR, and DOR, based on the same analysis methods described in Sections 4.4.1 and 4.4.2.

4.4.4 Sensitivity Analyses

A subsequent anti-cancer therapy for purposes of the sensitivity analysis is defined as any non• protocol specified treatment that the patient receives that is intended to treat her MBC prior to documented PD. A sensitivity analysis of investigator-assessed PFS for patients with detectable *PIK3CA*-mutant tumors will be performed, which censors

patient data at the last tumor assessment prior to initiation of subsequent anti-cancer therapy before PD.

4.4.5 Subgroup Analyses

Subgroup analyses (forest plot) of PFS and OS will be performed based on the stratification factors, demographics, and baseline prognostic factors.

4.5 PHARMACOKINETIC, PHARMACODYNAMIC, AND BIOMARKER ANALYSES

Taselisib plasma concentration versus time data will be tabulated and summarized. Additional analyses such as population pharmacokinetic analysis with covariate evaluation and assessment of exposure-response (i.e., efficacy, safety, and pharmacodynamics biomarkers) relationships may be conducted as appropriate. The results of these exploratory analyses will be reported separately from the CSR.

Exploratory biomarker analyses may be performed in an effort to understand the association of these markers with study treatment response. Results will be presented in a separate report from the CSR.

4.6 SAFETY ANALYSES

Safety analyses will be performed for the safety population, regardless of the *PIK3CA* mutation status of their tumors, and for the subgroup of patients with and without detectable *PIK3CA*-mutant tumors, with patients allocated to the regimen actually received.

Safety endpoints will include incidence and severity, outcome and seriousness of adverse events, death, laboratory data, and vital signs.

4.6.1 Exposure of Study Medication

Study treatment exposure (such as treatment duration, number of doses, dose reduction, and dose intensity) will be summarized for each treatment arm with descriptive statistics.

4.6.2 Adverse Events

Verbatim descriptions of adverse events will be mapped to MedDRA thesaurus terms and will be graded according to the National Cancer Institute Common Terminology Criteria for Adverse Events Version 4.0 (NCI CTCAE v4.0). Treatment-emergent adverse events (i.e., all adverse events that occurred on or after first dose of study drug and within 28 days after the last dose of study drug and related serious adverse events reported 28 days after the last dose of study drug) will be summarized by treatment arm and NCI CTCAE grade. In addition, serious adverse events, severe adverse events (Grade • 3), adverse events of special interest, and adverse events leading to study drug discontinuation, interruption, or reduction will be summarized accordingly. Multiple occurrences of the same event for a patient will be counted once at the maximum severity.

All deaths reported, deaths reported within (i.e., less than or equal to) 28 days of last dose of study drug, and deaths reported after 28 days of last dose of study treatment will be summarized separately by treatment arm, including the reasons for the deaths.

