Until approximately the end of August 2018, tumor assessments will be conducted for all patients 8 weeks (± 5 days) from the date of randomization and then every 8 weeks (± 5 days) thereafter, regardless of dose delays or dose interruptions, until 4–6 weeks after investigator-assessed disease progression or until death, whichever occurs first. After approximately the end of August 2018, tumor assessments may be conducted per local standard of care.

Patients may *remain on* study treatment until disease progression (as assessed by the investigator), unmanageable toxicity, or study termination by the Sponsor. Patients who discontinue taselesib/placebo due to toxicity may continue on single-agent fulvestrant at the discretion of the investigator. Discontinuation of fulvestrant for adverse events is very rare. However, in the unlikely event that the patient discontinues fulvestrant and is able to continue on taselesib/placebo, the investigator should contact the Medical Monitor to discuss the benefit-risk assessment of continuing with single-agent taselesib/placebo. All patients who are discontinued from all study treatment will return for a study drug discontinuation visit within 28 days after the last dose of study treatment (see [Section 4.5.10](#) for additional details).

Until approximately the end of August 2018, patients who are discontinued from study treatment for reasons other than disease progression will be asked to continue to have

tumor assessments performed and to complete the PRO assessments approximately every 8 weeks (± 5 days) until disease progression.

Until approximately the end of August 2018, after study treatment discontinuation, patients will be followed for survival and subsequent anti-cancer therapies approximately every 3 months until death, loss to follow-up, withdrawal of consent, or study termination by the Sponsor.

Until approximately the end of August 2018, after experiencing disease progression, patients will also be asked to return to the clinic approximately 4–6 weeks (for tumor and PRO assessments) and 12 weeks (± 1 week] for PRO assessments), even if a patient initiates anti-cancer therapy subsequent to study drug discontinuation.

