5.1.1.1.8 Infection

At the time of the primary PFS analysis of Study GO29058, 41.8% of patients in the tasisib arm had developed infections compared with 23.9% of patients in the control (placebo) arm. Serious infections occurred in 7.5% of patients in the tasisib arm compared with 0.9% of patients in the control (placebo) arm. A total of 0.5% of patients died on account of infection in the tasisib arm compared with no patients in the control (placebo) arm.

Urinary tract infections were the most commonly reported infection; however, respiratory tract, gastrointestinal tract, and skin infections were also common in the tasisib arm.

Investigators and patients should be aware of the increased risk of infection with tasisib. If a diagnosis of infection is made, appropriate treatment should be initiated promptly and consideration given to holding or discontinuing tasisib/placebo as per the guidelines in [Table 8](#).

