6.5 SAFETY ANALYSES

Safety analyses will be performed for all randomized patients who receive at least one dose of tselisib or placebo or fulvestrant (the safety population), regardless of the *PIK3CA*-mutation status of their tumors and separately for the subgroups of patients with and without detectable *PIK3CA*-mutant tumors, with patients allocated to the treatment arm associated with the regimen actually received. Specifically, a patient will be

included in the taselisib+fulvestrant arm in the safety analyses if the patient receives any amount of taselisib, regardless of the initial treatment assignment at randomization.

Safety endpoints will include incidence, severity, and relationship to the study drugs; outcome and seriousness of adverse events; death; laboratory data; and vital signs.

Drug exposure will be summarized to include duration of treatment, number of doses, and intensity of dose.

Adverse events will be summarized by mapped term, appropriate thesaurus level, and toxicity grade according to NCI CTCAE v4.0. All adverse events occurring during or after the first study drug dose will be summarized by treatment arm and NCI CTCAE grade. In addition, serious adverse events, severe adverse events (Grade ≥ 3), adverse events of special interest, and adverse events leading to study drug discontinuation or interruption will be summarized accordingly. Multiple occurrences of the same event will be counted once at the maximum severity.

Deaths reported during the study treatment period and those reported during the safety follow-up period (that is, within 28 days after the last dose of treatment) after treatment discontinuation will be summarized by treatment arm.

Laboratory data with values outside the normal ranges will be identified. In addition, selected laboratory data will be summarized by treatment arm and grade.

Clinically significant changes in vital signs will be summarized by treatment arm and grade.

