Table 2	Interim Analyses for Overall Survival if the First Interim Overall Survival Analysis Occurs at the Time of the Interim Efficacy Analysis of Investigator-Assessed Progression-Free Survival	13
Table 3	Interim Analyses for Overall Survival if the First Interim Overall Survival Analysis Occurs at the Time of the Final Efficacy Analysis of Investigator-Assessed Progression-Free Survival	14

LIST OF APPENDICES

Appendix 1	Protocol Synopsis	23
Appendix 2	Schedule of Assessments.....	33

1. **BACKGROUND**

Study GO29058 is a Phase III, double-blind, multicenter, randomized, placebo-controlled study designed to evaluate the efficacy and safety of taselisib + fulvestrant compared with placebo + fulvestrant in postmenopausal women with estrogen receptor-positive and human epidermal growth factor 2 (HER2)-negative locally advanced or metastatic breast cancer (MBC) who have disease recurrence or disease progression during or after aromatase inhibitor therapy.

Approximately 600 patients will be enrolled in the global study, including 480 patients with detectable *PIK3CA*-mutant tumors and 120 patients without detectable *PIK3CA*-mutant tumors. Patients will be randomized in a 2:1 ratio to receive either fulvestrant + taselisib or fulvestrant + placebo. Patients with and without detectable *PIK3CA*-mutant tumors will be randomized separately.

The primary efficacy endpoint is investigator-assessed progression-free survival (PFS) in patients with detectable *PIK3CA*-mutant tumors, and the secondary efficacy endpoints are overall objective response rate (ORR), overall survival (OS), clinical benefit rate (CBR), duration of objective response (DOR), and blinded independent central review (BICR)-assessed PFS in patients with detectable *PIK3CA*-mutant tumors. The safety of taselisib and fulvestrant compared with placebo and fulvestrant will be evaluated in patients with detectable *PIK3CA*-mutant tumors and also in all randomized patients who receive at least one dose of any component of protocol treatment (i.e., study drug).

The purpose of this Statistical Analysis Plan (SAP) is to provide the analysis plan proposed for this study by the Sponsor, F. Hoffmann-La Roche Ltd. The SAP overrides the analyses described in the statistical section of the protocol. The analyses as described in the SAP will be used by the Sponsor for the purpose of regulatory submission.

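### Adverse-event incidence is summarised only as crude patient percentages, although the observation window depends on time on treatment, so contrasts between arms may mix event rate with time at risk.

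*Combined protocol and SAP*

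**What the plan says.** SAP 4.6.2 defines treatment-emergent events as those from the first dose and "within 28 days after the last dose of study drug", plus related serious events reported later. They "will be summarized by treatment arm and NCI CTCAE grade", and "Multiple occurrences of the same event for a patient will be counted once at the maximum severity". Serious events, Grade ≥3 events, AESIs and events leading to discontinuation, interruption or reduction are handled the same way. Protocol 6.5 agrees: "All adverse events occurring during or after the first study drug dose will be summarized by treatment arm and NCI CTCAE grade".

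Three other passages fix the length of the window:

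- Protocol 3.1 lets patients stay on "study treatment until disease progression (as assessed by the investigator), unmanageable toxicity, or study termination by the Sponsor".
- SAP Section 1 uses the term study drug for any part of the regimen: "at least one dose of any component of protocol treatment (i.e., study drug". Fulvestrant therefore counts.
- Protocol 3.1 also allows patients who stop taselisib/placebo for toxicity to continue on fulvestrant alone.

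Exposure is reported, but separately. SAP 4.6.1: "Study treatment exposure (such as treatment duration, number of doses, dose reduction, and dose intensity) will be summarized for each treatment arm with descriptive statistics". No section uses it as a denominator for events. No test between arms is planned for adverse events.

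**The concern.** The safety objective (protocol 2.2) is one arm versus the other. The trial was designed around a large PFS gain (hazard ratio 0.59, control median 4.5 months), so unequal time on treatment was foreseeable when the SAP was written. The version 4 amendment rationale reports median PFS of 7.4 against 5.4 months. If patients on taselisib are observed longer, more of them will have a first event of a given kind even when the event rate is the same in both arms.

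A second mixture may act the other way. Adverse events led to discontinuation of taselisib/placebo in 16.8% against 2.3%. Those who then continued fulvestrant stay in the window while off taselisib, which would dilute effects confined to time on the drug.

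Crude percentages of this kind are used in the version 4 rationale to describe tolerability and in protocol 5.1.1.1.8 for infection, where 41.8% of the taselisib "arm had developed infections compared with 23.9% of patients in the control (placebo) arm". From such tables alone a reader cannot tell which mechanism acts on which event, or how strongly.

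**Working it through.** **The plan's own safety figure.** Protocol 6.1 gives a 96% probability of at least 10 patients with an event of 4% frequency among 400 treated. 1 − P(X ≤ 9), with X binomial(400, 0.04), is 0.960. It reproduces, and it is itself a crude patient proportion.

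**Inputs from the documents.** Median PFS 5.4 (placebo) and 7.4 months (taselisib), PIK3CA-mutant patients. Crude percentages, taselisib vs placebo: serious events 32.0 vs 8.9, Grade ≥3 49.5 vs 16.4, any infection 41.8 vs 23.9, serious infection 7.5 vs 0.9.

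**Assumptions.** Treatment duration and event follow-up by arm are not given. I take the event hazard h as constant, time on treatment as exponential with the PFS median (λ = ln 2 / median), and a tail w of 28 days (0.92 month). Then

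crude risk = 1 − [λ/(λ + h)] × exp(−h·w).

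λ is 0.693/5.4 = 0.1284 per month for placebo and 0.693/7.4 = 0.0937 for taselisib. The mean window, 1/λ + w, is 7.79 + 0.92 = 8.7 and 10.68 + 0.92 = 11.6 months, a ratio of 1.33.

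**Example, any infection.** For placebo, h = 0.0350 per month solves the equation: 1 − (0.1284/0.1634) × exp(−0.0350 × 0.92) = 1 − 0.786 × 0.968 = 0.239. The same h over the taselisib window gives 1 − (0.0937/0.1287) × 0.968 = 0.295. So 29.5 − 23.9 = 5.6 of the 41.8 − 23.9 = 17.9 points could arise with no difference in hazard.

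**All events, same steps.** The adjusted ratio solves h in each arm from its own crude percentage.

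| Event | Taselisib risk at placebo hazard | Points from longer window | Share of gap | Rate per 100 patient-years, taselisib vs placebo | Rate ratio | Crude ratio |
|---|---|---|---|---|---|---|
| Serious events | 11.5% | 2.6 of 23.1 | 11% | 47.0 vs 13.3 | 3.5 | 3.6 |
| Grade ≥3 | 20.7% | 4.3 of 33.1 | 13% | 94.6 vs 26.5 | 3.6 | 3.0 |
| Any infection | 29.5% | 5.6 of 17.9 | 31% | 70.6 vs 42.0 | 1.7 | 1.75 |
| Serious infection | 1.2% | 0.3 of 6.6 | about 5% | 8.3 vs 1.3 | about 6.7 | 8.3 |

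**Range.** I varied the medians (5.4/7.4 as reported; 5.4/7.71 from the hazard ratio of 0.70; 4.5/7.63 as planned) and left treatment time uncapped or capped at 12 or 6 months. The share of the gap runs from 3 to 20% for serious events, 4 to 23% for Grade ≥3 and 10 to 54% for any infection. The rate ratios run from 2.9 to 3.9, 3.0 to 3.7 and 1.4 to 1.9. The 54% comes from the planned medians, a larger PFS effect than the one reported.

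**Break-even.** For window length alone to explain the whole gap, the taselisib median would have to be about 28 months for serious events and about 13 months for any infection, against 7.4 reported.

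**The case against.** The strongest reply is that unequal observation time is itself an inference. The documents give no duration by arm. The PFS medians are for PIK3CA-mutant patients, while the safety population (SAP 4.1.2) covers all mutation statuses, and the amendment rationale does not say which population its percentages use. More toxicity stopping on taselisib narrows the imbalance in tablet exposure: about 9.0 vs 7.6 months (ratio 1.18) instead of 10.68 vs 7.79 (1.37). Events that occur early would hardly be affected by a longer window. All of this stands. It limits what can be said about size. It does not fill the gap in the plan, and stopping tablets does not close the window for a patient who continues fulvestrant.

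It is also fair that the tables are descriptive, that exposure is shown by arm, and that patient incidence is a legitimate description of what happens under each regimen as given. That is why the crude tables should stay. Two separate tables, however, do not let a reader recover a rate per event type.

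A reader might infer that part of the reported safety difference simply is longer follow-up, or that the infection guidance in protocol 5.1.1.1.8 rests on an artefact. The documents support neither. The first needs observation times and event timing that are not reported, and for Grade ≥3 events the adjusted ratio is larger than the crude one. Against the second, the same section also reports serious infections of 7.5% vs 0.9% and infection deaths of 0.5% vs none, and the serious-infection contrast is barely affected by window length.

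**Conclusion.** The point holds as a gap in the analysis plan. Adverse-event incidence is summarised only as crude patient percentages over a window tied to treatment duration, so contrasts between arms may mix event rate with time at risk. The likely effect is modest for serious and Grade ≥3 events. It could be larger for a common event that accrues over time: about 31% of the gap for any infection in the base case. In every case examined the excess on taselisib remains.

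All these sizes are illustrations. They rest on constant hazards, exponential treatment time and PFS standing in for time on treatment. The net direction of the bias for a given event cannot be determined from the documents, because a longer window and time off taselisib can pull in opposite directions. No safety conclusion in the protocol is overturned.

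**What to change.** In SAP 4.6.2, beside the crude tables:

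- Add the number of patients with a first event per 100 patient-years at risk, by arm, with the rate ratio and its 95% CI, for serious events, Grade ≥3 events, AESIs and infections. Infections need naming because they are not on the AESI list in protocol 5.2.3. Time at risk should end at the first event or at the close of the window.
- Repeat the AESI table with the window ending 28 days after the last taselisib/placebo dose, so that later time on fulvestrant alone is excluded.

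Cumulative incidence at 6 months with end of treatment as a competing event is not a substitute. With the same infection hazard in both arms (0.0350 per month) and the exit rates above, [h/(h + λ)] × [1 − exp(−6(h + λ))] still gives 13.4% for placebo and 14.6% for taselisib, so part of the artefact stays.

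The cost is a few supplementary tables from onset and dosing dates already collected. Patient-year rates are easiest to interpret when the hazard is roughly constant, so they supplement the crude incidence and do not replace it. As the primary analysis has already been run, the additions should be labelled supplementary.

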4.6.3 Laboratory Data

Selected laboratory data such as fasting glucose level, absolute neutrophil count, hemoglobin level, platelet count, lymphocyte count, serum creatinine level, and liver function test results (AST and ALT) with values outside the normal ranges will be summarized by treatment arm. For the selected laboratories, toxicity grade shift from baseline will be summarized by treatment arm.

4.6.4 Vital Signs

Change from baseline in vital signs will be summarized by treatment arm and grade.

4.7 MISSING DATA

For the analysis of OS, data from patients who are alive at the time of the analysis data cutoff will be censored at the last date they are known to be alive. Data from patients without post-baseline information will be censored at the date of randomization.

For the analyses of PFS and DOR, data from patients who are lost to follow-up or without disease progression or death as of the clinical data cutoff date will be censored at the time of the last tumor assessment when the patient is known to be progression-free (i.e., an overall response other than “progressive disease” or “not evaluable”) or at the time of randomization if there is no post-baseline tumor assessment or all post-baseline tumor assessments have overall responses of “not evaluable.”

For the FDA, the primary efficacy analysis for investigator-assessed PFS will be censored additionally for patients experiencing a progression event preceded by two or more missing tumor assessments before the disease progression (i.e., the duration between the date of first documented PD deemed by investigator per RECIST v1.1 and the date of the last tumor assessment when the patient is known to be progression-free > 122 days). These patients will be censored at the last tumor assessment prior to the missed visits that is known to be progression-free (i.e., an overall response other than “progressive disease,” or “not evaluable”) or at randomization if there is no post-baseline tumor assessment or all post-baseline tumor assessments have overall responses of “not evaluable” in between the randomization and the first documented PD per RECIST v 1.1.

For the analysis of ORR, patients with measurable disease at baseline but with no post-baseline tumor assessment or post-baseline tumor assessments that all have overall responses of “not evaluable” will be categorized as non-responders.

For the analysis of CBR, patients with no post-baseline overall response or post-baseline tumor assessments that all have overall responses of “not evaluable” will be considered to not experience clinical benefit.

For the EORTC QLQ-C30 and the modified breast cancer module QLQ-BR23 questionnaires, if $\geq 50\%$ of the constituent items are completed, a prorated score will be computed consistent with the scoring manuals and validation papers. For subscales with $< 50\%$ of the items completed, the subscale will be considered to be missing. If the additional items of the modified breast cancer module QLQ-BR23 (including oral mucositis and skin problems) have not been completed, they will be considered missing.

For the analysis of deterioration of HRQoL or global health scale, patients who have no definitive deterioration events (i.e., a decrease of ≥ 10 points from the Cycle 1, Day 1 scale score with no subsequent increase above this threshold) will be censored at the time of the last PRO assessment prior to disease progression.

4.8 INTERIM ANALYSES

The iDMC will convene to review cumulative safety data approximately every 6 months. Data on serious adverse events, death, and adverse events of special interest will be monitored by the iDMC approximately every 3 months.

One efficacy and futility analysis for investigator-assessed PFS will be conducted in patients with detectable *PIK3CA*-mutant tumors when approximately 172 investigator-assessed PFS events (approximately 60% of the information, expected at approximately 23 months after FPI) have occurred in patients with *PIK3CA*-mutant tumors. Approximately 320 patients with detectable *PIK3CA*-mutant tumors and approximately 120 patients without detectable *PIK3CA*-mutant tumors will have been randomized into the study by the time of the interim analysis. The actual timing of the interim analysis and the number of patients randomized will depend on the accrual rate and actual accumulation of PFS events observed in the study.

The iDMC will review the efficacy while the Sponsor and investigators remain blinded to the treatment assignment.

The iDMC may recommend stopping the study for efficacy at the interim efficacy analysis of investigator-assessed PFS, when the two-sided p-value $\leq 1.7 \cdot 10^{-5}$, with approximately 172 investigator-assessed PFS events at the interim efficacy analysis. The α -spending function is specified as Gamma ($\alpha = 16$), which allocates two-sided $\alpha = 1.7 \cdot 10^{-5}$ at the interim efficacy analysis when approximately 172 PFS events are reached and preserves the two-sided 1% α -level at the final PFS analysis. The actual boundary will be adjusted based on the actual number of investigator-assessed PFS events at the interim analysis. If the iDMC recommends stopping the study for efficacy at the interim analysis and the Sponsor decides to stop the study, the study team will be

unblinded, and the investigators and patients will remain blinded to individual patient-level treatment assignment until the final OS analysis.

The iDMC may recommend stopping the study for futility at the interim efficacy analysis of investigator-assessed PFS when the observed PFS HR is above 0.85, which provides a probability of 85% to stop the study if the true PFS HR is 1.0 (i.e., no treatment benefit). The purpose of the futility analysis is not to stop the study for a positive (significant) efficacy PFS outcome. Therefore, statistical significance level for the primary analysis of PFS does not need to be adjusted for this futility analysis to maintain the overall type I error control.

Three interim analyses for OS are planned in patients with detectable *PIK3CA*-mutant tumors based on the cobas[®] *PIK3CA* Mutation Test. The timing, expected number of deaths, and decision boundary at each interim analysis are described in Section 4.4.2.2. The type I error is under strong control by using the generalized Haybittle-Peto method (Haybittle 1971).

No formal interim analysis is planned for patients without detectable *PIK3CA*-mutant tumors.

The responsibility, membership, and communication flow of the iDMC are specified in the iDMC charter.

